x² = A plasma or urinary HCG in female subjects who are of child-bearing age will be collected within 7 days of study participation. While on study women of child-bearing age will have pregnancy test at each visit unless test has been performed within 24 hours of study visit

x³ = Patient may not use platelet inhibitors (e.g. clopidogrel) within 7 days or systemic anticoagulants (e.g. warfarin, enoxaparin, or DOAC) within 14 days of bronchoscopy.

X⁴ = Tuberculin skin test (TST) to placed prior to screening labs. A second TST may be completed per PI or designee if needed to confirm negative results one to three weeks after the first TST.

** = Bronchoscopy for visit 4 and visit 6 will be performed within 2 days after the PET-CT

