4 STUDY DESIGN

4.1 OVERALL DESIGN

Hypothesis

The major hypothesis of this single-site pilot study is that recruitment of antigen-specific T cells and innate immune cell subsets following bronchoscopic instillation of purified protein derivative (PPD) from *M. tuberculosis* into the lung will occur primarily in individuals with latent TB infection. These Mtb-specific T cell responses will occur only in the segments into which PPD was instilled and not in the control lung segments. Lastly, pulmonary immune cell activation and number will peak early after PPD instillation and subsequently wane both in the airways and peripheral blood. These responses will be much more pronounced in the local pulmonary micro-environment as opposed to the systemic vasculature.

Using PET-CT imaging after PPD instillation, we hypothesize that it will be possible to identify increased cellular activity in draining thoracic lymph nodes, as well as in the pulmonary parenchyma. Furthermore, we expect that the above signals we are able to discern will progressively wane in the weeks following bronchoscopic PPD instillation.

Longitudinal Study Design

We plan to screen up to 100 non-LTBI controls vs confirmed LTBI to enroll up to 25 individuals in order to have a total of 20 individuals who are concordant on the PPD and IGRA test complete the study as follows:

Group A (LTBI Group): 13 PPD + and IGRA + subjects

[figure not shown]
Group B (non-LTBI Group): 7 PPD - and IGRA - subjects

We seek to enroll individuals at a 2:1 ratio of Group A:Group B in order to maximize the data derived from individuals with latent TB who will mount antigen-specific T cell responses post PPD instillation. This strategy will also decrease variance in Group A via relative oversampling compared to Group B.

Figure 1 outlines the experimental timeline. A baseline PET-CT study of the thoracic cavity will be obtained, and the first bronchoscopy will be performed in the following the week to collect the baseline BAL sample and to instill the PPD as outlined above. Peripheral blood will be collected at the time of each bronchoscopy procedure before the BAL. To examine early immune responses, on approximately day 4 the second PET-CT study will be obtained and the following day a second BAL will be performed, and peripheral blood samples will be collected. BAL will be done first in the control anterior segment of the left upper lobe and then again in the

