8.2 EFFICACY ASSESSMENTS

8.2.1 Clinical Evaluations

Physical examination

History and physical examination with vital signs (weight, height, BMI, blood pressure, respirations, heart rate, temperature and oxygen saturation) will be performed at screening with focus on respiratory and cardiovascular systems. Repeat physical examinations with focus on respiratory and cardiovascular systems with vital sign measurements (blood pressure, respirations, heart rate, temperature and oxygen saturation) will be performed prior to each bronchoscopy.

Radiographic or other imaging assessments.

Chest PET-CT Scan

Subjects will undergo a total of 3 PET/CT scans. A baseline PET/CT of the chest will be performed no more than one week prior to the initial bronchoscopy (10). In order to examine early immune responses, on day 4 post instillation bronchoscopy, a second PET-CT scan will be obtained. Furthermore, in order to examine the persistence of immune cell metabolic activity in the pulmonary parenchyma and thoracic lymph nodes, a PET-CT image will be obtained on approximately day 20 post initial bronchoscopic challenge.

Each participant will be asked to provide an estimate of their radiation exposure within the calendar in order to assess if participation in the study will cause a participant to exceed his/her annual dose limit.

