A bronchoscope will be introduced via the trans-oral or trans-nasal route. Lidocaine will be instilled through the bronchoscope at the levels of the epiglottis, vocal cords, carina and mainstem bronchi to provide additional anesthesia during the procedure. A baseline (prior to control or PPD instillation) bronchoalveolar lavage (BAL) will be performed in the left superior lingular segment of the left upper lobe. The control instillation of normal saline will then be placed into the anterior segment of the left upper lobe. This instillation will be performed via introduction of a balloon-tipped 5-French pulmonary artery (PA) catheter (26). Next, the bronchoscope will be moved to the right lung, similarly, a baseline BAL will be performed in the right middle lobe medial segment. Immediately afterwards, tuberculin purified protein derivative will be instilled into the anterior segment of the right upper lobe via a separate 5-French balloon-tipped PA catheter. The bronchoscope will then be removed and the subject will recover and be monitored. If a subject requires additional monitoring they will be transferred to the Day Unit of the Clinical Center. Signs and symptoms for expected and unexpected responses from bronchoscopy and PPD instillation will be assessed during this time. At time of discharge their vital signs must return to baseline, the subject must be able to eat and drink without difficulty and have a responsible adult available for transport from the Clinical Center. Each participant will be called the following day to assess their respiratory status and evaluate for the development of any new pulmonary symptoms. If necessary, they will be re-evaluated at the Clinical Center by [name].

Provide Study Monitoring Plan:

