9.4 STATISTICAL ANALYSES

9.4.1 General Approach

Statistical analysis will be performed in R version 3.6.1 or later (CRAN.R-Project.org). For the analysis of primary and secondary endpoints, mixed effects models with repeated measure will be used to compare the LTBI and non-LTBI responses after bronchoscopic PPD instillation. For the primary hypothesis, the cell count for Mtb antigen-specific CD4+ and CD8+ T cells will be used as the response variable. Two separate statistical models will be entertained to explain the local pulmonary response and systemic vasculature, respectively. To guard against non-normal responses, a suitable data transformation on the response variable, e.g., log transform, will be performed if the original scale is highly skewed.

In regard to PET CT analysis, calculations for standardized uptake value will be made and normalized for scan differences using OsiriX MD (11). For the secondary hypothesis, the FDG SUV values from the PET CT image, measured at days -7, +4, and +20 days will be used as response in similar mixed effects models to study the group difference in average immunologic responses.

For the exploratory hypotheses, both numerical and graphical summary tools will be used to study the phenotypic and functional analysis of immune cell populations in the airways and circulation of individuals with or without LTBI. Also, descriptive statistics will be used to characterize the production of soluble mediators in BAL fluid and blood.

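### The PET-CT plan states only an LTBI versus non-LTBI contrast, so its within-person statements (right upper lobe avidity, rise then waning) cannot be separated from procedure effects

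*Combined protocol and SAP*

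**What the plan says.** **Analysis.** Section 9.4.1 states that the uptake values "measured at days -7, +4, and +20 days will be used as response in similar mixed effects models to study the group difference" in average response. Section 9.4.2 repeats that the models compare LTBI with non-LTBI. Neither section names a term for side, lobe or segment.

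**PET hypotheses.** Section 4.1 expects that after PPD "it will be possible to identify increased cellular activity in draining thoracic lymph nodes, as well as in the pulmonary parenchyma", and that these signals then fade over the following weeks. Section 9.1 expects significant avidity in the parenchyma and adjacent node of the right upper lobe area given PPD, largest in LTBI participants at day 4 and lower at day 20.

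**Order of scans and procedures.** Section 8.2.1 puts the baseline scan within the week before the first bronchoscopy. The schedule footnote in Section 1.3 adds: "Bronchoscopy for visit 4 and visit 6 will be performed within 2 days after the PET-CT". Each later scan therefore comes before the lavage of its own period. On day 0 (Section 8.3), on the left, baseline "bronchoalveolar lavage (BAL) will be performed in the left superior lingular segment of the left upper lobe". Then: "The control instillation of normal saline will then be placed into the anterior segment of the left upper lobe". On the right, "a baseline BAL will be performed in the right middle lobe medial segment", followed by PPD into the anterior segment of the right upper lobe. At day 5 (Section 4.1), "BAL will be done first in the control anterior segment of the left upper lobe and then again in the" matching right segment.

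**Control and regions.** Section 6.1.1 describes saline as the comparator for PPD. Section 4.1 brings the control segments into the T cell hypothesis but not the PET hypothesis. The synopsis limits the PET endpoint to adjacent parenchyma and draining nodes; the Section 3 table has all lung fields and the mediastinal nodes.

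**The concern.** The secondary objective is the location and persistence of immune activity. Both are statements about what happens within a person: where uptake rises, and whether it later falls. The written model answers a different question, namely whether the two groups differ.

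Only one scan per participant is free of instrumentation. If a reader judges the right upper lobe statement, or waning, from change since that scan, the change contains whatever balloon occlusion, instilled fluid and later lavage add to uptake. Section 2.1 describes FDG PET-CT as very sensitive to thoracic inflammation, so such a contribution cannot be assumed to be nil.

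At stake is attribution. Section 4.2 presents the scans as possibly the first localization of a non-infectious antigen challenge in humans. Section 2.3.2 would take early nodal activity as a reason to develop drugs that target thoracic nodes. Neither inference follows from a group difference alone.

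**Working it through.** **1. What each scan follows**

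| Scan | Right anterior segment (PPD) | Left anterior segment (saline) | Elsewhere |
|---|---|---|---|
| Day -7 | nothing | nothing | nothing |
| Day 4 | PPD instillation and flush | saline instillation and flush | day 0 lavage of right middle lobe and lingula |
| Day 20 | the same, plus day 5 lavage | the same, plus day 5 lavage | the same |

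Nominally the day 5 lavage lies 20 - 5 = 15 days before the day 20 scan. If the schedule's windows (-2/+3 and -5/+6 days) apply to those visits, the gap runs from (20 - 5) - (5 + 3) = 7 to (20 + 6) - (5 - 2) = 23 days.

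**2. What each contrast estimates.** For one region, write change from day -7 as P + A, where P is the procedure effect and A the PPD effect.

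- Group contrast: (P + A_LTBI) - (P + A_non) = A_LTBI - A_non. P cancels if equal in the groups.
- Within-group change on the right: P + A. Nothing cancels.
- Waning, day 20 minus day 4: (P20 - P4) + (A20 - A4). An instillation effect that fades looks like waning; residual lavage uptake at day 20 hides it.
- Right minus left anterior segment: (P_R - P_L) + A. P cancels if equal on the two sides.

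**3. Size.** The plan gives no power, alpha, SUV variability or procedure effect, so there is no figure of its own to reproduce. Everything here is illustrative: two-sided 5% tests, no PPD effect, and an assumed procedure shift d in SD units of the change.

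One-sample t test, noncentrality d√n. With n = 13 and d = 0.5 this is 0.5 × 3.61 = 1.80 on 12 df.

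| Assumed shift d | Right-only change, 13 LTBI | Planned group contrast, 13 vs 7 |
|---|---|---|
| 0 | 5% | 5% |
| 0.25 | 13% | 5% |
| 0.5 | 38% | 5% |
| 1.0 | 91% | 5% |

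The right-only test is not in Section 9; it stands for the inference a reader would draw informally. If P differed between groups by 0.25, 0.5 or 1.0 SD, the group contrast would be positive 8%, 17% or 52% of the time. With equal shifts on both sides, the simulated right-minus-left error rate is 4.9% to 5.0%; this follows from that assumption and is not independent evidence.

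**4. Precision of a side contrast.** SD of right minus left, relative to the right-only SD, is √(2(1 - r)), where r is the left-right correlation of change (not given). Detectable effects at 80% power, in SD of the change:

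| r | SD ratio | Right minus left, 13 LTBI | Group-by-side, 13 vs 7 |
|---|---|---|---|
| 0 | 1.41 | 1.20 | 1.96 |
| 0.25 | 1.22 | 1.04 | 1.70 |
| 0.5 | 1.00 | 0.85 | 1.39 |
| 0.75 | 0.71 | 0.60 | 0.98 |

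For reference, right-only change in 13 LTBI participants detects 0.85 SD and the planned group contrast 1.39 SD.

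**The case against.** A reader might infer that the planned PET comparison is itself biased, so that a group difference could be a bronchoscopy artefact. The documents do not support this. Both groups have the same lavages, saline, PPD and scans, and nothing in the plan suggests that procedure uptake differs by LTBI status. The part of the Section 9.1 hypothesis that expects the largest uptake in LTBI participants is served by the planned contrast.

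A reader might also infer that lavage contaminates the right upper lobe at day 4. It does not do so directly: the right-sided day 0 lavage is in the middle lobe, and the PPD segment is first lavaged at day 5. At day 4 the effect in that segment is from instillation; the nearby lavages matter mainly for nodes.

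Nor is the left lung simply ignored. Section 3 measures all lung fields, Section 9.4.7 lists data by location, and a model described only as similar does not exclude a side term. The study is also a hypothesis-generating pilot without formal power, and no section reports procedure-related uptake at day 4 or day 20.

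All of this stands. It narrows the point without removing it: the within-person statements are written as hypotheses, no analysis is named for them, and a pilot's signal is useful only if it can be attributed.

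**Conclusion.** The gap is real and limited to the within-person PET statements. Followed as written, the model can test whether LTBI and non-LTBI participants differ. It cannot test whether uptake is localized to the right upper lobe site, and it cannot separate a rise or waning within a group from instillation at day 4 or from instillation plus the day 5 lavage at day 20. A PPD or irritant effect common to both groups would also be invisible to the group contrast.

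The size of any distortion is unknown. The percentages above show how it would scale under assumed shifts and are not estimates for this trial.

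The side contrast rests on procedure effects being equal in the two anterior segments. That is plausible by design but not guaranteed: Section 6.1.2 gives a volume for the PPD dilution, and I find none for the saline control. For nodes the contrast is weaker, because the documents define no side-specific draining nodes and subtraction could remove real signal.

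**What to change.** In Section 9.4.1:

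- Keep the planned group comparison.
- For parenchyma, measure SUV on every scan in the anterior segment of the right upper lobe (PPD) and of the left upper lobe (saline). Use segments rather than lobes: the lingula lavaged on day 0 is part of the left upper lobe, whereas the right-sided day 0 lavage is outside the right upper lobe.
- Add side, time-by-side and group-by-time-by-side terms (with the lower-order terms they imply), and allow the two sides of one scan to be correlated.
- Base the right upper lobe statement on the right-versus-left change from day -7, and the waning statement on how that contrast moves from day 4 to day 20. Report single-side values alongside.
- Label any left-right nodal comparison as supportive only.
- Reconcile the synopsis with the Section 3 table on which regions are measured; under the synopsis wording the left segment might not be read.

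Cost: SAP wording and one further region analysed on scans already planned, with no new scan, visit or radiation. The side contrast has a wider interval than the right side alone if the left-right correlation of change is below 0.5, up to 1.41 times the SD at zero correlation.

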9.4.2 Analysis of the Primary and Secondary Endpoints

For the analysis of primary and secondary endpoints, mixed effects models with repeated measure will be used to compare the LTBI and non-LTBI responses after bronchoscopic PPD instillation.

For the primary hypothesis, the cell count for Mtb antigen-specific CD4+ and CD8+ T cells will be used as the response variable. Two separate statistical models will be entertained to explain the local pulmonary response and systemic vasculature, respectively. To guard against non-normal responses, a suitable data transformation on the response variable, e.g., log transform, will be performed if the original scale is highly skewed.

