3 OBJECTIVES AND ENDPOINTS

OBJECTIVES	ENDPOINTS	JUSTIFICATION FOR ENDPOINTS
Primary		
The primary objective of this study is to understand the pulmonary immune response to mycobacterial antigens by determining the persistence of antigen-specific immune cells in the airways versus circulation after local bronchoscopic instillation of PPD into the lungs of adults with or without LTBI.	The primary endpoint will be the enumeration of Mtb antigen-specific CD4+ and CD8+ T cell populations in the airway and peripheral blood at early and late time points after bronchoscopic PPD instillation.	This endpoint is chosen to determine the point after directed bronchoscopic exposure to Mtb peptide the antigen-specific T cell response is strongest both locally in the lung and systemically in the blood.
Secondary		
The secondary objective is to characterize the location and persistence of immune cell activity in the pulmonary parenchyma and thoracic lymph nodes with positron emission tomography combined with chest computed tomography (PET-CT) after bronchoscopic PPD instillation in adults with or without LTBI.	The secondary study endpoint of this study is the quantification of FDG SUV throughout all lung fields and mediastinal lymph nodes of LTBI and non-LTBI patients at days -7, +4, and +20 after PPD bronchoscopic instillation.	This endpoint is chosen in order to identify and track over time the geographically anatomic distribution of immune cell activity in the lungs after PPD instillation.
Exploratory		
The exploratory objectives of this study are (a) to perform phenotypic and functional analysis of immune cell populations in the airways vs circulation following bronchoscopic instillation of PPD into the lungs of individuals with or without LTBI, (b) to characterize the production of soluble mediators (i.e. cytokines, lipid mediators, defensins) in BAL	(a) An exploratory endpoint will be the quantification of frequencies of cell surface molecules, intracellular cytokines and transcription factors among immune cell populations in the airways vs circulation following bronchoscopic instillation of PPD into the lungs of individuals with or without LTBI. (b) An exploratory endpoint will involve the	These endpoints are chosen to characterize the cellular phenotype and function of the most influential immune cell populations within the context of pulmonary tuberculosis in the local lung micro-

OBJECTIVES	ENDPOINTS	JUSTIFICATION FOR ENDPOINTS

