9 STATISTICAL CONSIDERATIONS

9.1 STATISTICAL HYPOTHESIS

- *Primary Endpoint:*
We hypothesize that antigen-specific CD4+ T cells response will be highest in the BAL five days post challenge in LTBI subjects alone and may subsequently wane 21 days post challenge.
- *Secondary Endpoint:*
We hypothesize that there will be significant FDG-avidity within the lung parenchyma and adjacent thoracic lymph node within the area of the lung (right upper lobe) in which PPD is selectively instilled. We expect that the SUV quantities will be most pronounced in LTBI subjects at day 4 post challenge and subsequently wane at day 20.
- *Exploratory Endpoints:*

We hypothesize that the phenotype and function of Mtb-specific T cells in the BAL will differ from that of circulating T cells. We hypothesize that bronchoscopic instillation of PPD will induce production of TH1 predominant pro-inflammatory cytokines, eicosanoid lipid mediators and defensins in the local airway environment more so than the systemic vasculature. We hypothesize that these soluble mediators will be primarily present in LTBI subjects on day 5 post challenge and wane at day 20.

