9.4.8 Exploratory Analyses

For the exploratory hypotheses, both numerical and graphical summary tools will be used to study the phenotypic and functional analysis of immune cell populations in the airways and

circulation of individuals with or without LTBI. Also, descriptive statistics will be used to characterize the production of soluble mediators in BAL fluid and blood.

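### The primary objective compares the airways with the circulation, but section 9.4.2 plans no airway-versus-blood estimate or interval for the primary T-cell count

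*Combined protocol and SAP*

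**What the plan says.** - **Objective.** Section 3, like the Synopsis, gives the primary aim as "determining the persistence of antigen-specific immune cells in the airways versus circulation after local bronchoscopic instillation of PPD", in adults with or without LTBI. The endpoint is the number of Mtb-specific CD4+ and CD8+ T cells in airway and blood, early and late.
- **Justification column, section 3.** It asks at what point "the antigen-specific T cell response is strongest both locally in the lung and systemically in the blood".
- **Design hypothesis, section 4.1.** After describing an early peak and later waning, it adds: "These responses will be much more pronounced in the local pulmonary micro-environment as opposed to the systemic vasculature".
- **Statistical hypothesis, section 9.1.** "antigen-specific CD4+ T cells response will be highest in the BAL five days post challenge in LTBI subjects alone".
- **Analysis, section 9.4.2, repeated in 9.4.1.** "mixed effects models with repeated measure will be used to compare the LTBI and non-LTBI responses after bronchoscopic PPD instillation". "Two separate statistical models will be entertained to explain the local pulmonary response and systemic vasculature, respectively". The response is a cell count with no stated unit or denominator, and "a suitable data transformation on the response variable, e.g., log transform, will be performed if the original scale is highly skewed".
- **Elsewhere.** Section 9.4.8 says that "both numerical and graphical summary tools will be used to study the phenotypic and functional analysis of immune cell populations in the airways" and in circulation. Section 9.4.7 lists each person's values by measurement, site and day. Section 9.3 names no analysis population.
- **Size.** Section 9.2 sets 13 LTBI and 7 non-LTBI participants, calls the study a hypothesis-generating pilot, and makes no power calculation.

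**The concern.** The primary objective names a contrast between two compartments of the same person. The planned primary analysis estimates a contrast between two groups of people, once in the lung and once in the blood. If the plan is followed as written, the lung-against-blood part of the objective, and the directional sentence in 4.1, would rest on reading two model outputs side by side.

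That reading has two weaknesses. Blood and BAL come from the same person on the same day, so the uncertainty of their difference depends on the airway-blood covariance, which two separate models do not estimate. The transformation rule also depends on skew, so one compartment could be analysed on the log scale and the other not. A pilot needs no powered test of its main question, but it should give an estimate with an interval to carry forward.

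**Working it through.** **Step 1. Match each statement to a planned analysis.**

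| Question | Where stated | Planned analysis |
|---|---|---|
| LTBI versus non-LTBI within lung or within blood | 4.1, 9.1 | Yes, 9.4.2 |
| Timing within each compartment | Section 3 justification, 9.1 | Can be read from the repeated-measures models |
| Airway versus blood, primary count | Objective (1.1, 3); one sentence in 4.1 | None; individual listings only (9.4.7) |
| Airway versus blood, phenotype and function | Exploratory, 9.1 | Descriptive summaries, 9.4.8 |

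No joint model, compartment term, paired difference or ratio appears in 9.4.1 or 9.4.2.

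**Step 2. Are the samples paired?** Yes. Section 4.1 takes blood at each bronchoscopy before the BAL, and section 8.2.3 gives days 0, 5 and 21. The PPD segment is lavaged on days 5 and 21. Baseline BAL comes from the lingula and the right middle lobe (8.3), not from the challenged segment, so a day 0 airway value is not a same-site baseline.

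**Step 3. Which scale is needed?** On the log scale, day 21 minus day 5 is a log fold change. Any fixed unit cancels within its compartment, so the two changes can be compared without a shared denominator. A one-day level has no such cancellation and needs one common unit.

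**Step 4. Precision.** The plan has no SD, correlation, alpha or power, so there is no figure of its own to reproduce beyond 13 + 7 = 20 and 20 + 5 = 25. Everything below is illustrative, with SD 1 in each compartment.

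*Day 5 level, airway minus blood.* Half-width = t(0.975, n-1) × sqrt(2(1-r)/n), where r is the airway-blood correlation. For n = 13, t = 2.179:
- r = -0.3: 2.179 × sqrt(2.6/13) = 0.97 SD
- r = 0: 2.179 × sqrt(2/13) = 0.85 SD
- r = 0.6: 2.179 × sqrt(0.8/13) = 0.54 SD

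*Day 21 minus day 5 change, airway minus blood.* Each compartment's change has variance 2(1-w), where w is the day-to-day correlation. With correlation c between the two changes, half-width = t × sqrt(4(1-w)(1-c)/n). For n = 13:

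| | c = -0.3 | c = 0 | c = 0.6 |
|---|---|---|---|
| w = 0.3 | 2.179 × sqrt(3.64/13) = 1.15 | 2.179 × sqrt(2.8/13) = 1.01 | 2.179 × sqrt(1.12/13) = 0.64 |
| w = 0.6 | 2.179 × sqrt(2.08/13) = 0.87 | 2.179 × sqrt(1.6/13) = 0.76 | 2.179 × sqrt(0.64/13) = 0.48 |

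*Non-LTBI, n = 7, t = 2.447.* Day 5 level: 2.447 × sqrt(2.6/7) = 1.49 down to 2.447 × sqrt(0.8/7) = 0.83 SD. Change: 2.447 × sqrt(3.64/7) = 1.76 down to 2.447 × sqrt(0.64/7) = 0.74 SD.

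**Step 5. What separate models lose.** Treating the two models as independent gives an interval 1/sqrt(1-r) times the correct one (c replaces r for the change). The factor is 0.88 at -0.3, 1.00 at 0, 1.41 at 0.5 and 1.58 at 0.6. At zero correlation nothing is lost. The correlation is unknown, so the direction of the error is unknown too.

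**The case against.** The best defence is that most of the plan asks about timing and group within each compartment. The justification column asks when the response peaks in lung and in blood. The sentence in 9.1 reads naturally as a statement about day and group within BAL. This stands: a reader might infer that 9.1 and the justification column also demand a compartment comparison, but their wording does not require it. The clear support is the objective and the one sentence in 4.1.

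Second, the study is a pilot with 20 completers, and the listings in 9.4.7 would let a reader see paired values. This narrows the consequence, but a listing gives neither an estimate nor an interval. Section 9.2 waives a power calculation, not estimation of the objective.

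Third, one might infer that airway and blood cannot be compared at all because no common unit is given. That goes too far. The gap in units affects one-day levels, and it matters if only one compartment is transformed. A log fold change avoids it.

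Fourth, the half-widths show how precise the added contrast would be, not how much harm the present plan does. That is right, and they are used only in that sense. If changes in the two compartments are uncorrelated and on the same scale, a joint analysis gains essentially nothing over adding the variances from the two models. The contrast would still have to be specified.

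**Conclusion.** The point holds as a gap between objective and analysis. Sections 9.4.1 and 9.4.2 plan no airway-versus-blood estimate or interval for the primary count, although the primary objective names that comparison.

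The gap does not make the two planned models wrong: they answer the questions on group and timing, and they should stay. Nor does it show that the study is too small for its purpose, since no power is claimed.

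For the 13 LTBI participants, the change contrast would have a half-width of 1.15 to 0.48 SD and the day 5 level 0.97 to 0.54 SD. That is enough to describe large differences. With 7 non-LTBI participants, at 1.76 to 0.74 SD for the change, the contrast is descriptive only. These ranges assume equal SDs, complete pairs and the correlations shown, none of which comes from the protocol. Unequal SDs would change them.

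A reader might also expect a comparison of the PPD segment with the saline segment to close the gap. It would not: at one visit the blood value cancels, leaving a within-lung effect. That is a different hypothesis in 4.1, and it is optional here.

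**What to change.** Keep both models and add to 9.4.2 a pre-specified, estimation-only, within-person contrast of PPD-segment BAL against blood in LTBI participants, for CD4+ and CD8+ separately, with 95% intervals.

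- **Main contrast:** the day 21 versus day 5 change, on the log scale in both compartments whatever the skew, with a stated rule for zero counts.
- **Supportive contrast:** the day 5 level, only on one named common unit, for example share of parent CD4+ or CD8+ cells if parent counts are kept, which the protocol does not state. A level also carries standing differences between compartments, so it should not be read as response to PPD alone.
- **Method:** a paired analysis, or a joint model with within-person covariance and unequal compartment variances.
- **Population:** participants who received PPD and have paired samples at the visit (at both visits for the change), with the number missing shown.
- **Non-LTBI:** the same quantities, shown descriptively.
- **Day 0:** no airway change from day 0 without a note that baseline BAL came from other segments.

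The cost is SAP wording and a little analysis, with no new samples. It adds 2 contrasts × 2 cell types = 4 intervals in LTBI participants. They will be wide and without multiplicity control, and should be labelled as estimation in a hypothesis-generating pilot. If the sponsor intends the lung-against-blood comparison to be descriptive only, the objective and 9.4.2 should say so.
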